3.4 Smoking Outcomes

Smoking Rate (TLFB). We will assess the number of cigarettes smoked on each day throughout the study. A standard timeline follow-back (TLFB) method will be used [67], as we have done previously [68] to assess self-reported smoking rate. During each quit week, abstinence will be assessed daily by self-report of no smoking at all over the prior 24 hours and an expired-air CO less than 5 ppm (except for the Monday visit when CO may be less than 10ppm or less than 50% Baseline CO). This stringent biochemical criterion for validating smoking cessation has been shown to be more sensitive to detect smoking and specific to verify abstinence than higher CO cut-offs [69].

Carbon Monoxide. Carbon monoxide (CO) measures will be made using a Vitalograph Breath CO Analyzer (McNeil International, Inc., Lenexa, KS). The manufacturer will have calibrated this device within the past year. A new, disposable cardboard mouthpiece will be provided for each participant. The device has a digital screen which reports CO levels in parts per million (ppm). Participants will be asked to provide a CO breath sample by taking a large breath then exhaling twice. Then, they will take another deep breath and hold their breath for 10 seconds, as per the recommendations of the American Thoracic Society. Then, when instructed to do so, participants will exhale as forcefully and as long as they are comfortably capable. The largest value displayed is recorded during all CO breath samples. CO breath samples will be collected at each study visit. At the Intake, participants must have CO readings greater than or equal to 10ppm in order to be eligible for the study.

2. Statistical Analysis

Sample size.

Effect sizes for power analyses were derived from prior work on TN effects on days of abstinence (Aim 1) [6], studies demonstrating RAM's effects on sleep (Aim 2), and our preliminary data. All significance levels will be set at 0.05. Our primary hypothesis is that RAM will increase the number of days abstinent (out of 5), compared to placebo. In prior validation work, the average number of days abstinent for TN was 2.0 ± 0.3 [6]. Fifty subjects provide 80% power to detect a difference of 0.55 days between RAM and PLA, using a SD of 1.36 and a within-subjects correlation of 0.78 [31].

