For Aim 2, meta-analyses indicate that RAM is associated with reducing SOL by 4.3 min and increasing sleep efficiency by 4.42% [70]. Our preliminary data suggest that TN increases sleep disturbance by 58% ($d=0.28$) in abstinent smokers and that abstinence increases SOL by ~5 min and decreases sleep efficiency by ~5%. Fifty subjects provide 80% power to detect differences of 6 min in SOL and 5% in sleep efficiency between RAM and PLA, using a within-subject correlation between 0.4 and 0.8. Thus, Aims 1 and 2 are sufficiently powered.

Statistical Analysis.

For Aim 1 (H1), a within-subject ANOVA will test the primary hypothesis for effects of RAM (vs. PLA) on number of days abstinent during the quit week.

For Aim 2 (H2a), separate 2 drug (RAM vs. PLA) x 2 week (baseline vs. quit week) repeated measures ANOVAs will test the effects of RAM on SOL and sleep efficiency. Drug and week are within-subject factors and sleep measures will be averaged across days within each baseline and quit week. We are primarily interested in the drug x week interaction to test whether RAM (vs. placebo) attenuates sleep disturbance during the quit week, relative to baseline. Thus, each period has its own baseline control comparison. A supplemental analysis will include only days during the quit week when subjects are abstinent.

For Aim H2b, linear regression models will test whether sleep disturbance predicts number of days abstinent and

whether this relationship varies by treatment. Models will include covariates (e.g., baseline depression/anxiety, FTND, sex, and age). We will also examine correlations between sleep disturbance data and nicotine withdrawal and depression/anxiety symptoms in both groups.

3. Confidentiality

All participant information will be kept in a secure filing cabinet that is accessible only to authorized study personnel. All study databases containing participant information will be password protected, and accessible only to authorized study personnel. Any study communications made by e-mail will use ID numbers and not include names or other personal information. All data sets will use ID numbers only.

How will confidentiality of data be maintained? Check all that apply.

- Paper-based records will be kept in a secure location and only be accessible to personnel involved in the study.
- Computer-based files will only be made available to personnel involved in the study through the use of access privileges and passwords.

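### The H2a sleep test subtracts each baseline in full; adjusting for the same baselines estimates the same effect and, apart from the degrees of freedom used, is never less precise

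*Combined protocol and SAP*

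**What the plan says.** The section 2. Statistical Analysis (which follows 3.4 Smoking Outcomes) sets out H2a for sleep onset latency (SOL) and sleep efficiency: "separate 2 drug (RAM vs. PLA) x 2 week (baseline vs. quit week) repeated measures ANOVAs will test the effects of RAM". Nightly values are first reduced to weekly means: "sleep measures will be averaged across days within each baseline and quit week". The test of interest is named: "We are primarily interested in the drug x week interaction to test whether RAM (vs. placebo) attenuates sleep disturbance during the quit week". The stated reason for the structure is that "Thus, each period has its own baseline control comparison".

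Covariates are named only for H2b. No baseline-adjusted version of H2a appears anywhere.

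The Aim 2 power statement, under the Sample size subheading, reads "Fifty subjects provide 80% power to detect differences of 6 min in SOL and 5% in sleep efficiency between RAM and PLA". It takes the correlation within a person to be anywhere from 0.4 to 0.8. It gives no SD, does not name the interaction, and does not say which pair of weeks the correlation describes.

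**The concern.** Each participant contributes four weekly means: baseline and quit week, on ramelteon (RAM) and on placebo (PLA). The interaction is (quit minus baseline on RAM) minus (quit minus baseline on PLA), which forces a weight of exactly 1 on the baseline difference. That weight is best only if the regression slope of the quit-week difference on the baseline difference happens to be 1. If the slope is smaller, full subtraction adds baseline noise to the drug contrast. It can even do worse than leaving the baselines out.

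Sleep is the mechanism the trial is built on, and H2a is its direct test. Avoidable noise raises the chance of missing a real sleep effect in a pilot meant to inform a larger trial. The plan has little precision to spare on SOL: the meta-analytic effect it cites is 4.3 min, below the 6 min it claims to detect.

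**Working it through.** **Inputs from the plan.** N = 50; 80% power; 6 min for SOL and 5% for sleep efficiency; within-subject correlation 0.4 to 0.8. On alpha: "All significance levels will be set at 0.05". Sidedness is not stated, so two-sided is assumed.

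**The plan's own figure.** The 80% cannot be reproduced, because no SD is given. It can only be solved backwards. For a paired t-test with n = 50, the difference detectable with 80% power is 0.404 times the SD of the paired differences. So 6 min implies an SD of 6/0.404 = 14.8 min, and 5% implies 5/0.404 = 12.4%.

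**Variances.** Let D_Q and D_B be a participant's RAM-PLA differences in the quit-week and baseline means, with common variance V and correlation r.

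- Interaction, D_Q - D_B: 2V(1 - r)
- D_Q adjusted for D_B: V(1 - r²)
- D_Q alone: V
- Ratio of interaction to adjusted: 2(1 - r)/(1 - r²) = 2/(1 + r)

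The interaction beats D_Q alone only when 2(1 - r) < 1, that is, when r > 0.5.

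**Unequal SDs.** With k = SD(D_B)/SD(D_Q), the ratio is (1 + k² - 2rk)/(1 - r²). The numerator minus the denominator is (k - r)², which is never negative. So, before counting degrees of freedom, adjustment is never less precise. Two examples:

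- k = 0.8, r = 0.5: (1 + 0.64 - 0.8)/0.75 = 1.12
- k = 1.25, r = 0: 1 + 1.5625 = 2.56

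**What r could be.** r is not the plan's within-subject correlation, because differencing across periods removes stable differences between people. If all cross-period correlations are equal, r = (same-period - cross-period)/(1 - cross-period). With equal SDs and values taken from 0.4 to 0.8:

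| Same-period | Cross-period | r | Ratio |
|---|---|---|---|
| equal to cross-period | any | 0 | 2.00 |
| 0.6 | 0.5 | 0.20 | 1.67 |
| 0.7 | 0.5 | 0.40 | 1.43 |
| 0.8 | 0.6 | 0.50 | 1.33 |
| 0.8 | 0.4 | 0.667 | 1.20 |

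Simulation with n = 50 and 20,000 runs per setting gave ratios of 1.95, 1.65, 1.39, 1.30 and 1.18 for these rows. Both estimators averaged 6.0 min for a true effect of 6 min.

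**Power, illustration only.** This depends on which contrast the plan's 80% describes.

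*Reading A: the simple quit-week difference (SD 14.8 min).* The interaction SD is 14.8 × √(2(1 - r)): 21.0 min at r = 0 and 14.8 min at r = 0.5. Interaction power is from the noncentral t; adjusted power is from the simulation, in which the slope is estimated.

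| r | Interaction | Adjusted |
|---|---|---|
| 0 | 51% | 79% |
| 0.2 | 60% | 81% |
| 0.4 | 72% | 86% |
| 0.5 | 80% | 89% |

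The N for 80% power with the interaction is 99 at r = 0 and 50 at r = 0.5.

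*Reading B: the interaction itself.* The planned test then has 80% power at every r. By the variance formula, adjustment raises this to about 98% at r = 0, 94% at r = 0.25 and 90% at r = 0.5.

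**The case against.** The strongest reply is that the planned test is valid and answers the question asked, namely change relative to baseline. The 2 x 2 layout also shows whether withdrawal disturbed sleep at all, and the outcomes are secondary in a proof-of-concept pilot. All of that stands. The point is one of efficiency only.

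The ratio rests on quantities the plan does not give, and that also stands. The value 2.0 needs all four weekly means to be equally correlated. Weeks within a period are adjacent (1-2, 5-6), while weeks in different periods are three to five weeks apart, so some positive r is plausible. Neither r nor equality of the SDs can be read from the documents.

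A reader might infer that Aim 2 is underpowered, at 51% say. The documents do not support this. That figure needs Reading A, and the power sentence does not say which contrast it describes. Under Reading B the planned test keeps its 80%.

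A reader might also infer that a disturbed week-5 baseline biases the interaction. With balanced order, a shift common to both sequences does not. Bias needs differential carryover, which nothing in the plan demonstrates; the plan has a two-week washout with return to smoking.

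One objection changes the remedy. The interaction cancels a period shift shared by baseline and quit week; an adjusted model without a period term does not. If p is the shared shift, m the order imbalance among completers and b the slope, a bias of m × p × (1 - b) remains. It is probably small, but enrolment runs until 50 people complete and attrition is expected, so exact balance is not assured. The adjusted model should therefore include period.

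**Conclusion.** The concern holds as a loss of efficiency, and correcting it is a free improvement. Absent differential carryover, baseline adjustment estimates the same effect as the planned interaction and, apart from the degrees of freedom used, is never less precise. That conclusion needs no value for r.

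The size does. With equal SDs and same-period and cross-period correlations within 0.4 to 0.8 (same-period at least as high), the interaction has about 1.2 to 2.0 times the variance, and so needs about that many times the participants for equal precision. Unequal SDs widen this, for example to 1.12 or 2.56. The power values are conditional illustrations, not findings about the trial. The planned test should not be described as biased or invalid.

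**What to change.** For each sleep outcome, define the H2a test as the drug term in a mixed model of the quit-week mean on drug, period and that period's baseline-week mean, with a random participant effect. Enter the baseline mean as two terms: the within-person deviation and the person's mean. Equivalently, regress each participant's RAM-PLA quit-week difference on the RAM-PLA baseline difference and a sequence indicator coded +1/-1 and centred, and test the intercept. Report the 2 x 2 interaction as a supplement.

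The Aim 2 power statement should also say which contrast it describes and give the SD it uses.

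The cost is SAP wording and about two degrees of freedom. No new data, visits or participants are needed.

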- a. Sleep disturbance measures (sleep onset latency and sleep efficiency) with ramelteon treatment vs. placebo.
- b. Predicting the ability to remain abstinent during the 5-day quit assessment week based on reduction in withdrawal-related sleep disturbance.

BACKGROUND

There is a Critical Need for Novel Smoking Cessation Treatments. Despite the fact that cigarette smoking continues to be the greatest preventable cause of morbidity and mortality, there are currently only three FDA-approved medications for nicotine dependence: nicotine replacement therapy (NRT; transdermal nicotine (TN), nasal spray, gum, lozenge), bupropion, and varenicline. Although TN doubles the odds of smoking cessation compared to placebo, the majority relapse within the first week [1, 2]. Importantly, we demonstrated that each additional day of abstinence during the first week nearly doubles the odds of success at end-of-treatment [3]. There is a clear need to identify novel approaches to optimize treatment to help more smokers maintain abstinence during this critical period. The development of a clinically valid model for early human screening of medications to treat nicotine dependence [4-6], coupled with an emphasis on “repurposing” existing medications, provides a practical approach to achieve this aim [7, 8]. These models can also be used to assess novel smoking cessation treatment targets, such as sleep disturbance.

Sleep Disturbance is a Treatment Target. Converging lines of evidence suggest that remediating sleep disturbance may be a novel therapeutic target as an adjunct treatment for nicotine dependence. First, nicotine withdrawal is associated with sleep disturbance, such as difficulty falling asleep and increased number of awakenings [9-11]. Second, existing nicotine dependence treatments do not mitigate sleep problems during a quit attempt; in fact, we and others have shown that TN [12-15] and varenicline [16] may exacerbate the problem. Third, sleep disturbance predicts smoking relapse in clinical trials and laboratory models of relapse [17-19]. Our preliminary data demonstrate that smokers who report longer sleep onset latency and wake more often are abstinent for fewer days using a model of short-term abstinence.

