Participants will be recruited from two sources. Participants who have previously completed studies at our center and have agreed to be re-contacted for future studies will be contacted and invited to participate in this study. Additional recruitment via TV, newspaper, radio, poster, and internet-based advertising (e.g., in-app ads, Craigslist, and iConnect) will be used to invite smokers from the general population.

STUDY DESIGN

1. Phase

Phase: II Randomized, double-blind, placebo-controlled trial

Figure 1. Overview of Study Design

PHASE	INTAKE	STUDY PERIOD 1					WASHOUT	STUDY PERIOD 2										
WEEK #	0	Baseline 1			Quit Week 2		3-4	Baseline 5			Quit Week 6							
STUDY VISITS	X	M	W	F	M	T	W	TH	F	NONE	M	W	F	M	T	W	TH	F
MEDICATION	NONE			*RAM plus TN or PLA plus TN		NONE WASHOUT			*RAM plus TN or PLA plus TN									
ACTIVITY	Medical History Psych Screen	Monitoring Visits Sleep Monitoring		Observation Assessments Sleep Monitoring		NONE			Monitoring Visits Sleep Monitoring	Observation Assessments Sleep Monitoring								
SMOKING STATE	Smoking Ad Libitum			Monitored Abstinence		Smoking Ad Libitum			Monitored Abstinence									

* Treatment (RAM vs PLA) order randomized and counterbalanced across subjects; All subjects receive transdermal nicotine (TN). TQD=Target Quit Date

2. Design

We propose to conduct a randomized, placebo-controlled, cross-over design with one within-subjects factor of medication (RAM vs. PLA; order counterbalanced). Each phase includes: 1 week of *ad libitum* smoking (baseline) and 1 week of medication (8mg RAM or PLA) plus TN while trying to abstain (quit assessment) (Figure 1).

3. Study Duration

Estimated length of time to enroll all subjects and complete the study

Enrollment will start in October 2015 (after IRB approval is received). We estimate that we will need to telephone screen 1500 smokers to enroll (consent) 150 smokers into the study (accounting for 10% eligibility). Using a conservative estimate of attrition (50%), we expect to have 50 participants complete all sessions and study requirements. We estimate enrolling 4-5 smokers per month.

Length of a subject’s participation time in study

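### H2b names ordinary linear regression with no participant effect, so its test of whether the sleep–abstinence relation differs by treatment does not use the crossover pairing and loses power

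*Combined protocol and SAP*

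**What the plan says.** The analyses are in section 2, Statistical Analysis, which follows 3.4 Smoking Outcomes. The design is a "cross-over design with one within-subjects factor of medication (RAM vs. PLA; order counterbalanced" (Study Design, 2. Design), so each completer contributes two quit weeks, one per treatment.

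- **H1:** "a within-subject ANOVA will test the primary hypothesis".
- **H2a:** "Drug and week are within-subject factors", and "Thus, each period has its own baseline control comparison".
- **H2b:** "linear regression models will test whether sleep disturbance predicts number of days abstinent", and "whether this relationship varies by treatment". On adjustment: "Models will include covariates (e.g., baseline depression/anxiety, FTND, sex, and age". These are all participant-level terms.

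No participant effect, clustered variance or mixed model is named for H2b. The text does not say whether the two quit weeks are stacked in one model or fitted by arm, and it does not define the sleep predictor. Objectives, 3. Secondary Outcome Variable(s), item b, describes prediction "based on reduction in withdrawal-related sleep disturbance". Read with H2a's own-baseline comparison, this points to a change score within each period. No power figure or effect size is given for H2b.

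**The concern.** H2b tests the proposed mechanism: that less sleep disturbance goes with more abstinence, and that this link may differ under ramelteon. In a crossover, comparing the link between treatments compares two slopes in the same people. Ordinary regression treats the two quit weeks as coming from different people. Stable between-person differences in abstinence then stay in the error term, and a real treatment difference in the link is easier to miss.

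If rows are pooled, the test of the treatment-averaged slope is affected in the other direction. When sleep change is positively correlated across periods, a chance association is declared somewhat too often. The stake is a mechanism result from a pilot that is meant to inform a larger trial.

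**Working it through.** **Inputs from the plan.** 50 completers, so 100 quit-week rows; significance level 0.05 (two-sided assumed); SD 1.36 and within-subject correlation 0.78 for days abstinent; 0.4 to 0.8 for the sleep measures (Sample size).

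**The plan's own figure first.** Fifty subjects are said to give 80% power for 0.55 days.
- With 1.36 as the SD of the paired difference, a paired t-test gives 80.0%. If 1.36 is also the per-week SD, then 1.36 = 1.36 × √(2(1 − r)), so r = 0.5.
- With 1.36 as the per-week SD and r = 0.78, the SD of the difference is 1.36 × √0.44 = 0.902 and power is 98.8%.

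The outcome correlation is therefore uncertain, and both 0.78 and 0.5 are carried through.

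**Assumed, not in the documents.** The cross-period correlation of the change score (rx = 0, 0.2, 0.3) and the H2b slope difference.

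**Size.** Let re be the residual correlation between a person's two quit weeks. The two rows carry opposite treatment codes, so in pooled regression the true-to-nominal SE ratio is √(1 − rx·re) for sleep × treatment and √(1 + rx·re) for the treatment-averaged slope. At rx = 0.3, re = 0.78:
- rx·re = 0.234.
- Interaction: √0.766 = 0.875; 1.96/0.875 = 2.24; true error 2.5%.
- Averaged slope: √1.234 = 1.111; 1.96/1.111 = 1.76; true error 7.8%.

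At rx = 0 both ratios are 1 and there is no size error.

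**Power for the interaction.** Setting covariates aside, pooled regression's nominal variance exceeds the paired model's by R = (1 + rx·re)/(1 − re²). Take an effect with 80% power under the paired model (1.96 + 0.84 = 2.80 standard errors).
- re = 0.78, rx = 0: R = 1/0.3916 = 2.55; 2.80/√2.55 = 1.75; power about 42%.
- re = 0.78, rx = 0.3: R = 1.234/0.3916 = 3.15; 2.80/√3.15 = 1.58; (1.58 − 1.96)/0.875 = −0.44; about 33%.
- re = 0.5, rx = 0: R = 1/0.75 = 1.33; 2.80/√1.33 = 2.43; about 68%.
- re = 0.5, rx = 0.3: R = 1.15/0.75 = 1.53; 2.80/√1.53 = 2.26; (2.26 − 1.96)/√0.85 = 0.33; about 63%.

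**Simulation.** 50 pairs, four null participant-level covariates, 10,000 null runs and 4,000 power runs per setting. The slope difference was set for about 80% mixed-model power: 0.50/0.46/0.45 days per SD of sleep at outcome r 0.78, and 0.69/0.66/0.64 at 0.5.

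| Outcome r | Sleep-change r | Interaction error, pooled | Averaged-slope error, pooled | Interaction power, pooled | Interaction power, mixed |
|---|---|---|---|---|---|
| 0.78 | 0 | 5.1% | 5.0% | 43.1% | 78.7% |
| 0.78 | 0.2 | 3.1% | 7.2% | 36.5% | 79.0% |
| 0.78 | 0.3 | 2.5% | 7.8% | 34.5% | 77.8% |
| 0.5 | 0 | 5.0% | 4.9% | 67.2% | 78.1% |
| 0.5 | 0.2 | 3.8% | 6.4% | 63.4% | 78.0% |
| 0.5 | 0.3 | 3.1% | 6.6% | 63.3% | 79.0% |

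A repeat simulation gave pooled power of 35–44% and 63–68% against 79–80%.

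**Arms fitted separately.** Each arm's own slope test is valid (4.7–5.4%), as is the placebo slope under 0/1 coding (4.8–5.5%). Comparing the two slopes as if independent gives 5.2/3.1/2.7% at outcome r 0.78 and 4.9/3.9/3.0% at 0.5 for sleep r 0/0.2/0.3, much as in the pooled case.

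**If quit-week sleep levels were the predictor.** Taking the plan's 0.4–0.8 as the cross-period correlation (also an assumption), interaction error falls from 1.6% to 0.2% and averaged-slope error rises from 9.4% to 12.4% at outcome r 0.78. At 0.5 the ranges are 3.0% to 1.3% and 7.6% to 9.8%.

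**Sensitivity.** Rounding and bounding the outcome to 0–5 days, or letting covariates explain 20% of outcome variance, leaves the direction unchanged.

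**The case against.** The plan is silent rather than wrong. It does not say that rows are pooled, it speaks of models in the plural, and its covariate list is only by example. This stands: a reader might infer that all of H2b is invalid, but under separate fits each arm's slope test is sound, and only the comparison between treatments is affected. Silence does not cure that comparison, because the method named does not use the pairing under either reading, while the same section names within-subject methods for H1 and H2a.

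A reader might also take 0.2% and 12.4% as the size of the problem. Those figures need quit-week levels as the predictor; the wording of the objectives and of H2a points to change from own baseline, where the distortion is modest and vanishes at zero correlation. The power loss remains even there.

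The power contrast rests on a large assumed effect (0.45–0.69 days per SD of sleep, beside the 0.55-day effect for H1). For 0.27 days per SD and sleep r of 0 to 0.3, the mixed model had only 36–41% power at outcome r 0.78 and about 23% at 0.5, against 14–19% for pooled regression. A paired model does not by itself make H2b adequately powered.

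Finally, a mixed model with a single sleep slope leans on within-person variation. With a purely between-person slope of 0.4 outcome SD per SD of sleep, at outcome r 0.78 and sleep r of 0 to 0.3, it detected the averaged slope in 9–15% of runs, against 42–65% for pooled regression. This also stands, and it shapes the fix.

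**Conclusion.** The concern holds for the treatment comparison in H2b. Ordinary regression does not use the pairing, so it loses power at any cross-period sleep correlation in the range examined, and it is conservative when that correlation is positive. For a change score with an assumed correlation of 0 to 0.3, interaction error is about 5% down to 2.5%. If rows are pooled, averaged-slope error is about 5% up to 8%. Where a paired model has about 79% power, pooled regression has about 35–44% (outcome r 0.78) or 63–68% (0.5).

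The direction follows from the design. The sizes rest on the assumed change-score correlations, on an H2b effect that the documents do not give, and on which outcome correlation applies. H1 and H2a are unaffected, and H2b is a secondary aim of a pilot study. The change is worth making but is not critical to the trial's main result.

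**What to change.** Replace the H2b regression with a linear mixed model for days abstinent per quit week, one for sleep onset latency and one for sleep efficiency:

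- **Participant:** random intercept.
- **Sleep:** that period's quit-week mean minus its own baseline-week mean, entered as two terms: the participant's mean over the two periods (between-person) and the deviation from that mean (within-person).
- **Other fixed effects:** treatment (coded −0.5/+0.5), period, sleep × treatment (the product of treatment with the change score itself), and the listed covariates.
- **Inference:** state which sleep slope answers the prediction question, and test sleep × treatment in the same model with Satterthwaite or Kenward-Roger degrees of freedom.

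In simulation the split model kept error at about 4–6% for every term and interaction power at about 79–80%. It detected the purely between-person slope in 49–62% of runs, where the unsplit mixed model managed 9–15%. The calibration runs for the unsplit model used a fixed t on 91 degrees of freedom, so the small-sample correction itself was not tested there.

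Clustered standard errors on the ordinary regression would not be enough. At zero sleep correlation, outcome r 0.78 and an assumed slope difference of 0.4 residual SD, interaction power was 51% with them, 49% without, and 85% with a paired model.

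Cost: SAP wording, minor code, one more model term and a slightly less simple H2b result. No new data, visits or participants.
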